3. METHODS AND STUDY DESIGN

3.1 Aims and Objectives

To undertake a pilot RCT as a precursor to a fully-powered non-inferiority RCT. The pilot will determine rates of participant recruitment, randomisation, treatment and research attrition and completeness of outcome data prior to establishing whether a fully-powered non-inferiority RCT is feasible.

The external pilot RCT will:

1: Determine the rate of trial recruitment, retention in treatment and research, understand reason for drop out and determine completeness of outcome data assessed against progression criteria to determine if a fully powered trial is deliverable;

2: Undertake exploratory analyses of the outcome data to support a power calculation for a fully powered non-inferiority trial;

3: Understand the safety risks;

4: Establish an expanded mental healthcare capacity across Northern Ireland to enable both interventions to be delivered close to the veteran's home.

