3.6 Sample Size

The proposed external pilot sample size takes into account published recommendations for pilot trials (42, 43) which propose a method for determining an external pilot RCT sample size in order to minimise the sample size for the main RCT. This sample size will support the calculation of confidence intervals around the proportion of eligible participants who agree to take part in the research, and the attrition rates from both the treatments and the research. Our proposed sample size is 60, 30 in each arm. Initially, we had a 1:1 randomisation ratio. However, with 50% of our target randomisation figures achieved due to therapist attrition in the TF-CBT delivery arm we sought statistical advice and decided to change the randomisation ratio to 2:1 in favour of the experimental RTM. This would allow us to continue to recruit at the level required to fulfil our recruitment targets specified by our funder.

Treatment seeking in the veteran population is low (44, 45) and response rates to PTSD research invitations are poorly reported (46, 47). For example, Ulmer et al (2011) (48) screened 91 veterans with PTSD to recruit 22 participants to their pilot RCT. In a review of 7 randomised trials comparing TF-CBT with Eye Movement Desensitisation and Reprocessing, research and treatment attrition ranged from 8 - 58% with a mean of 29% (49). Taking these data into account, we propose to screen 180 people for eligibility, randomise 60 participants and expect an attrition of 30% and 50% (or lower) from the intervention and comparison respectively resulting in \geq 36 participants with data at 20 weeks follow up. A screening sample of 180 would be sufficient to obtain a 95% confidence interval for a

proportion of $\pm 8\%$ or narrower, and a sample of 60 for a 95% confidence interval of $\pm 13\%$ or narrower, both with 99.9% probability calculated using SAS POWER (50)

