3.14 Statistical Data Analysis

We will calculate rates of recruitment, willingness to participate, proportions of participants with PTSD and complex PTSD, intervention and research drop-out rates. Estimates of variability (standard deviation) of outcome assessments will be used to inform the sample size calculation for the future fully powered non-inferiority RCT. We expect to use a non-inferiority margin for PCL-C of five. A similar conservative margin was proposed by Foa *et al* (2018) (77) for PCL-5 based on Monson *et al* (2008)(78). Prior to making this calculation the main study outcome(s) will be examined to see whether they conform reasonably well to a normal distribution. If not a transformation of the data will be considered. SAS procedure POWER (50) will be used to calculate the sample size estimate for a comprehensive follow-on non-inferiority RCT (42). Exploratory analyses will enable the standard deviation of changes in pilot outcome assessments to be calculated using appropriate statistical methods (e.g. random effects regression models).

Because the change of randomisation ratio took place mid-way through the trial when 50% of the target number of randomisations had already occurred on a 1:1 ratio, the analysis of participant data before (1:1 ratio) and following (2:1 ratio) the allocation change will need be undertaken separately.

The study will use King's CTU standardised operating procedures as appropriate, as follows:

- 1. Data monitoring committee
- 2. Statistical analysis plan
- 3. Statistical documentation retention
- 4. Statistical QA
- 5. Sample size calculation
- 6. Protocol review and blinding
- 7. Statistical reports
- 8. Data manipulation following data extraction

We will follow the CONSORT guidance for pilot and feasibility trials and for intervention studies and the TIDieR checklist (79, 80).

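### The change from 1:1 to 2:1 allocation does not require separate analysis of the two phases; a phase-stratified analysis of all 60 is valid and more precise

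*Protocol*

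**What the plan says.** Section 3.6 (Sample Size) gives the target: "Our proposed sample size is 60, 30 in each arm". It then reports that, "with 50% of our target randomisation figures achieved", loss of therapists in the TF-CBT arm led the team to "change the randomisation ratio to 2:1 in favour of the experimental RTM".

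Section 3.14 (Statistical Data Analysis) draws a consequence for the analysis: "the analysis of participant data before (1:1 ratio) and following (2:1 ratio) the allocation change will need be undertaken separately". The only reason given is the change of ratio. No stratified, adjusted or combined analysis is described.

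Other parts of the protocol are written for the trial as a whole:

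- Section 3.1 sets as its second objective: "Undertake exploratory analyses of the outcome data to support a power calculation for a fully powered non-inferiority trial". Section 3.14 describes a single sample size calculation for that trial.
- Section 3.6 justifies the sample size by the precision of a proportion estimated on all 60 participants.
- Section 3.2 (question e) and Appendix 4 set treatment-completion or drop-out thresholds per arm, none of them by phase.

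**The concern.** A change of allocation ratio creates one real hazard. The RTM share rises from 50% to 67% over calendar time, so a crude comparison of all RTM with all TF-CBT participants would mix any time trend into the arm difference. Each phase, however, is a randomised comparison in its own right. Estimating the arm difference within phase and combining the two estimates removes that hazard. Separate analysis is therefore not needed, and it has a price.

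Read as it stands, the sentence yields two SDs, two effect estimates and two drop-out rates per arm. The protocol has one main-trial sample size to calculate and one drop-out threshold per arm to judge. It does not say how two estimates would be merged, or what follows if one phase meets a threshold and the other does not. At stake is the precision of the quantities that the pilot was set up to supply.

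**Working it through.** **Inputs.** The target is 60, the change comes at 50% of target, and the ratio is then 2:1 in favour of RTM (section 3.6). These imply about 30 participants at 1:1 (15 RTM, 15 TF-CBT) and 30 at 2:1 (20 RTM, 10 TF-CBT), in total 35 and 25. The cells are implied, not stated. For attrition, section 3.6 says the team "expect an attrition of 30% and 50% (or lower) from the intervention and comparison respectively". I apply those rates equally in both phases and assume a common outcome variance.

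**The plan's own figures.**
- Retention: 30 × 0.70 + 30 × 0.50 = 36, as stated.
- Worst-case 95% half-width of a proportion, 1.96 × √(0.25/n): 12.65 points for n = 60, consistent with the stated 13. The exact (Clopper-Pearson) maximum is 13.2.

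**Precision of a proportion by phase.** The same formula with n = 30 gives 17.9 points. By arm:

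| Arm | Whole trial | 1:1 phase | 2:1 phase |
|---|---|---|---|
| RTM | 16.6 (n = 35) | 25.3 (n = 15) | 21.9 (n = 20) |
| TF-CBT | 19.6 (n = 25) | 25.3 (n = 15) | 31.0 (n = 10) |

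**Standard error of an arm difference, in SD units, before attrition.**
- 1:1 phase: √(1/15 + 1/15) = 0.365
- 2:1 phase: √(1/20 + 1/10) = 0.387
- Stratified by phase, inverse-variance weights: √(1/(1/0.1333 + 1/0.15)) = 0.266
- Crude pooling: √(1/35 + 1/25) = 0.262

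The separate standard errors are 1.37 and 1.46 times the stratified one. Stratifying costs about 1.5% against crude pooling.

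**Precision of the SD at 20 weeks.** Expected numbers with data:
- 1:1 phase: 15 × 0.70 + 15 × 0.50 = 18
- 2:1 phase: 20 × 0.70 + 10 × 0.50 = 19, of whom only 5 are TF-CBT

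The 95% limits for the SD are the estimate times √(df/χ²), with df equal to participants minus cells:

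| Analysis | df | 95% limits (× SD) |
|---|---|---|
| 1:1 phase alone | 18 − 2 = 16 | 0.745 to 1.522 |
| 2:1 phase alone | 19 − 2 = 17 | 0.750 to 1.499 |
| Pooled within arm and phase | 37 − 4 = 33 | 0.807 to 1.316 |
| Two arms, ignoring phase | 37 − 2 = 35 | 0.811 to 1.304 |

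For a fixed margin, error rate and power, the main-trial size scales with the SD squared. The limits for the implied size, as a multiple of the point value, are therefore 0.745² to 1.522² = 0.56 to 2.3 for the 1:1 phase alone, and 0.807² to 1.316² = 0.65 to 1.73 pooled within phase.

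Before attrition the corresponding df are 28 per phase, 56 pooled within phase (60 − 4) and 58 ignoring phase. Stratification costs two df in either case.

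**The case against.** Three stronger readings are tempting, and the documents do not support them.

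- **That no progression criterion could be judged.** Most criteria in Appendix 4 are whole-trial counts: 180 identified, 60 randomised, 36 retained at 20 weeks, and 54, 42 and 30 complete data sets. Counts add across phases however the outcomes are analysed. Only the arm-specific drop-out or completion rates are exposed, and even their numerators and denominators can be summed. Section 3.14 does not say that the feasibility rates in its opening lines will be split.
- **That half the information on the SD is lost.** This is so only if the two estimates stay apart. Pooling the two within-phase variances recovers 56 of 58 df before attrition, and a stratified contrast is itself a weighted combination of two within-phase contrasts. The protocol provides no such step, but it does not forbid one.
- **That two inconsistent main-trial sample sizes would result.** Two imprecise SDs need not conflict, and section 3.14 speaks of one calculation.

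It can also be said that the SAP, which is not shown, may contain a combining rule, and that results by phase have a legitimate use. The ratio changed because TF-CBT therapists were lost, so TF-CBT delivery and drop-out may differ between phases. Both points stand. The second is a reason to report by phase as well, not instead. The first does not rescue the sentence: the protocol does more than leave a detail open, since it declares separate analysis necessary for a reason that does not make it so, and a SAP that combined the phases would have to depart from it.

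**Conclusion.** The concern holds in a limited form. The ratio change does not require separate analysis, and the rule in section 3.14 is less precise than an equally valid alternative that costs about two degrees of freedom. The standard error of an arm difference is 37% and 46% larger by phase than stratified. Neither phase meets the precision that section 3.6 plans for 60 participants. If the phase estimates are left uncombined, the 20-week SD rests on about half the degrees of freedom.

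Affected are the arm-specific drop-out or completion rates, the SD and the effect estimate; the whole-trial counts are not. The figures rest on the implied 15/15 and 20/10 cells, on the planned attrition holding in both phases, and on a common variance. Combining improves precision without making it good: TF-CBT drop-out on all 25 still has a worst-case half-width of 19.6 points. Because this is an external pilot with exploratory outcome analyses and no confirmatory comparison, the point should be fixed but does not threaten the trial.

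**What to change.** Replace the sentence in section 3.14 with:

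> All randomised participants are analysed together. Between-arm comparisons are stratified by or adjusted for allocation phase (1:1, 2:1). The SD for the main-trial sample size is pooled from the within-arm, within-phase variances. Progression criteria are judged on the whole trial, using total counts per arm against the per-arm thresholds; any between-arm comparison of drop-out is stratified by phase. Results by phase, including drop-out per arm, are also reported, because the TF-CBT therapist attrition that prompted the change may have affected delivery.

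Two details matter. The SD must come from the four arm-by-phase cells, because a single phase covariate does not give a within-arm, within-phase SD. Summing counts per arm is acceptable for judging an arm against a fixed threshold, but it would be crude pooling if the two totals were then compared between arms.

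The cost is one paragraph and about two degrees of freedom. Randomisation, data collection and participant burden do not change. The SAP should carry the same rule.

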3.15 Project Management and Investigator Expertise

Our research brings together a unique collaboration of academic, charity, NLP training and public involvement organisations who are expertly placed to safely deliver and evaluate the RTM therapy and the research protocol. [name], [name], [name] and [name] (King's College London, King's Clinical Trials Unit) and [name] (Queen's University Belfast) will lead the research evaluation, with their combined expertise in veteran populations, mental health, behavioural sciences and clinical trials. Inspire (formerly The Northern Ireland Association for Mental Health) is our charity partner and

clinical provider. Inspire has robust clinical, financial and information governance policies and procedures in place to conduct this study. [name] (Queen's University Belfast) will deliver the public involvement activity, to ensure the views of veterans and their families are represented throughout the research design and delivery. The RTM protocol therapist training and quality assurance will be undertaken by international NLP expert, [name] of Awaken Consulting. The TF-CBT protocol therapist training and quality assurance will be undertaken by [name], CBT/EMDR Therapist and Service Manager, Military Veterans' Service.

3.15.1 Study Management

The co-principal Investigators, [name] and [name], will assume overall responsibility for the research. The Study Group (SG) will hold fortnightly virtual meetings between the King's team and the QUB team. [name] and [name] support a 60% project manager/researcher at KCL. [name] supports a 60% researcher based at QUB respectively to formally recruit and undertake most of the data collection. These meetings will have standing agenda items relating to recruitment, data completion, intervention commencement and the detection and management of adverse events. Other team members will attend by request of the PI as required. [name] has experience of developing and delivering complex interventions and working with others to undertake data collection in multiple and remote research sites around the country and internationally. The team has been assembled largely using good communication methods across considerable geographical distance and the detailed project management and governance arrangements are robust to monitor activity to time, budget and protocol and to be flexible and adaptable to necessary changes. All investigators have roles and responsibilities that will keep them in at least bi-weekly contact with the project leads and the researchers. We have costed in 20 individual flights and overnight stays for the London/England team to have a physical presence in Belfast, commencing in the early stages of the project when the collaborative relationships are consolidating.

The whole research team will form the Project Management Group (PMG), consisting of investigators, collaborators, two members of our public involvement group, and representatives of a four-member charity stakeholder group. The PMG will meet quarterly in months 0, 4, 8, 12, 16, 20, 24 and 28 over the 28-month study duration. We will offer virtual meeting arrangements to maximise attendance. We will establish a stakeholder group of 4 UK-based charity representatives to engage with electronically and in-person throughout the research to ensure the views of the veteran charity sector are represented.

3.15.2 Data Monitoring and Ethics Committee (DMEC)

We have established a TSG and DMEC which have agreed to meet jointly on four occasions during the trial. The DMEC will review the unblinded data with the study statistician with regard to participant safety. They will then report to the TSG with any recommendations to take forward.

3.15.3 Participant Safety and Risk Management

Participant safety will be a standing agenda item of each fortnightly King's-QUB meetings. We additionally propose to fund an independent, Northern Ireland based, trauma-experienced Clinical Psychologist for up to 50 hours in total for the 18 months of the RTM intervention delivery and follow-up period. This Independent Clinical Psychologist will provide an independent safety net for participants and their family if they become concerned about a participant's mental health. No such events have been identified in the five USA trials of RTM so we believe this time allocation will be sufficient for this purpose. This Clinical Psychologist will also have independent access to the DMEC chair.

3.15.4 Data management

A web based electronic data capture (EDC) system has been designed, using the InferMed Macro 4 system. The EDC will be created in collaboration with the trial analyst/s and the CI and maintained by the King's Clinical Trials Unit for the duration of the project. It will be hosted on a dedicated secure server within KCL.

The CI or delegate will request usernames and passwords from the KCTU. Database access will be strictly restricted through user-specific passwords to the authorised research team members. It is a legal requirement that passwords to the EDC are not shared, and that only those authorised to access the system are allowed to do so. If new staff members join the study, a user-specific username and password must be requested via the CI or delegate (e.g. Trial Manager) from the KCTU team and a request for access to be revoked must be requested when staff members leave the project. Study site staff experiencing issues with system access or functionality should contact the CI or delegate (e.g. Trial Manager) in the first instance.

No identifiable data beyond participant initials and age at consent will be entered on the EDC or transferred to the KCTU. No data will be entered onto the EDC system unless a participant has signed a consent form to participate in the trial. Source data will be entered by a researcher or Inspire nominated individual, typically within eight days of data collection by authorised staff onto the EDC by going to www.ctu.co.uk and clicking the link to access the MACRO 4 EDC system. A full audit trial of data entry and any subsequent changes to entered data will be automatically date and time stamped, alongside information about the user making the entry/changes within the system.

The CI team will undertake appropriate reviews of the entered data, in consultation with the project analyst, for the purpose of data cleaning and will request amendments as required.

At the end of the trial, the site PI will review all the data for each participant and provide electronic sign-off to verify that all the data are complete and correct. At this point, all data can be formally locked for analysis.

Upon request, KCTU will provide a copy of the final exported dataset to the CI in .csv format and the CI will onward distribute as appropriate.

4. PROJECT OUTPUTS

4.1 Impact

The major impact of this research will be the submission of a funding application for the full noninferiority RCT. We will begin the development of this full application as soon as 50% of our target sample have completed the intervention and 12-week follow up. This will give us sufficient evidence to deploy our traffic light progression criteria towards a full trial funding application.

We consider that the best interests of people living with PTSD will be served if the fully powered RCT is designed to engage with the NHS. The NIHR South London Research Design Service has confirmed that our proposed phase III trial is within the funding remit of two NIHR research programmes: Health Technology Assessment (HTA), and Programme Grants for Applied Research (PGfAR). These programmes are currently participating in the **Promotion of good mental health and the prevention or treatment of mental ill health NIHR** themed call. These programmes focus on clinical intervention

delivery by NHS and non-NHS providers and therapists. We propose the following population (P), intervention (I), comparison (C) and outcome (O) plan for a phase III trial:

P - Military veterans and ex non-military uniformed services

- I RTM protocol
- **C -** TF-CBT

O - PTSD symptoms assessed by the Post-traumatic stress disorder checklist for DSM-5 (PCL- 5) and functional capacity as assessed by the Work and Social Adjustment Scale (WSAS)

4.1.1 Fully powered trial progression criteria

See appendix 4.

4.2 Dissemination

The proposed study is an external pilot RCT and we expect one major peer-reviewed paper to be developed from this study for publication in an open access journal. Funding has been requested for this purpose. This paper will present the pilot evidence relating to the intervention delivery and the research protocol performance. The target journal for this will be the BMC Open Access journal *Pilot and Feasibility Studies*. A further paper may be developed to propose a logic model for the RTM protocol intervention for submission to *Journal of Traumatic Stress* (Impact Factor 2.72) or *Psychological Trauma: Theory, Research, Practice and Policy* (Impact factor 2.30). NHS veteran and mental health conferences will be targeted for conference presentation and the INVOLVE conference to discuss our project outcomes/outputs through an Involvement lens.

Appendix 1: Participant safeguarding protocol

Our experimental therapy, RTM protocol, has been delivered without serious adverse event in five USA studies involving over 120 veterans (28, 31-33, 53). Nonetheless, it is important to have a robust safety protocol for this vulnerable group of UK participants for its first exposure to a UK population. The following comprises our safety protocol for all participants in the trial, throughout the trial, and specifically for all participants randomised to the experimental RTM group. It addresses lines of responsibility and accountability, definitions relating to safety, escalation and safeguarding procedures in the event of notable clinical deterioration with or without an escalation in risk, alongside ensuring the safe and effective management of participants who are ineligible to enter the trial.

1.0 Lines of responsibility and accountability

- 1.1 From the point at which a potential participant is handed over to Inspire for eligibility assessment through to the point of discharge, Inspire have responsibility and clinical governance accountability for the participant's mental health and wellbeing and including their own safety and where relevant the safety of others and including the safeguarding of children and vulnerable adults.
- 1.2 From the point of discharge from Inspire therapy to the point of 52 week follow, up or withdrawal from the trial, the participant's GP holds responsibility and accountability for the participant's mental health and wellbeing and this includes their safety.
- 1.3 Participant safety will be a standing agenda item on every fortnightly King's- QUB research team meeting.
- 1.4 Data Monitoring and Ethics Committee (DMEC) will meet four times during the trial comprising three trauma experts, a veteran welfare expert and an independent statistician. The DMEC terms of reference will operate according to the King's Clinical Trials Unit Standard Operating Procedures. The research team will report any participant safety issues to the DMEC within 48 hrs of each fortnightly King's and Queen's meeting.

